- Diagnosis and procedures associated with hospital admission
- Death date (if applicable)
- Discharge date (if applicable)

Phase II.B: Post COVID-19 diagnosis data: Study participants only

- Infusion date (i.e., date at which drug is administered)
- History of adverse effects (if any)
- Details of adverse effects (if any)
- Types of adverse effects (Based on Optum Infusion nurse data/ProtectWell assessment score of 1-10)
- Date of experiencing adverse effect(s) (if applicable)
- Drop-out date (If available)
- Drop-out reason (if applicable)

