4.2 Data Collection

The data sources for study participants and the pool of potential controls are not all the same because we don't enroll matched controls in this study. To make sure both groups are symptomatic, we will use Optum electronic medical record (EMR) data to select symptomatic COVID-19 cases as candidates of control, while this information for study participants comes from ProtectWell symptoms data. We summarize the data sources for study participants and matched controls in Table 1.

For enrolled participants, tracked data collection begins from first report of symptoms via ProtectWell. The data collection timepoints are:

1. First report of symptoms
2. COVID-19 test result (positive – moves forward; negative – resets the experience)
3. Date of receipt of Bamlanivimab (LY3819253) via infusion (Day 1)
4. Day 1 infusion (pre, during, post) collection of CRF data (participant vitals/health information and any events experienced)
5. Day 1 post-infusion baseline wellness check through Day 28 final wellness check
6. Any point during Day 1 post-infusion baseline through Day 28 where wellness check indicates participant is feeling worse
7. Point from participant marking feeling worse through action taken (live daily check-in via clinical support, recommendation to seek medical care and/or requiring hospitalization)

Regarding the timeline, the overall duration for enrolled participants is up to 6 months with symptom tracking only. Once an enrolled participant becomes a study participant after reporting symptoms, it is up to 38 days (28 days of active participation after receipt of infusion on Day 1 and up to 10 days from report of symptoms to receive infusion). For matched controls, the active insurance coverage after date of symptoms onset should be up to 38 days. We require matched controls to remain enrolled in utilized data sources to assure data availability. Similar to enrolled participants, matched controls may die after the synthetic date of treatment.

Commented [WWY1]: Would suggest to add A figure to illustrate study design, including screening and treatment time point and assessment period

Commented [JAT2R1]: Thanks for the suggestion. I added a sentence directing the audience to Figures 2 and 3 on the screening process and timeline.

Table 1. Main data sources of study participants and the potential pool of controls.

Study population	Data name	Data description

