Study participants	Optum infusion pharmacy data	Day 1 at-home infusion will collect vitals and other essential data pre, during and post-infusion using an established case report form (CRF) to collect any events experienced during and post-infusion related to Bamlanivimab (LY3819253)
	ProtectWell data	during symptom tracking – status of what was selected per daily check-in, first trigger point of noting experiencing symptoms, if COVID-19 positive and received infusion – Day 1-28 wellness tracking (in numeric 1-10 ratings)
	UHC claims data (UHC members only)	data including demographic characteristics (e.g., age, gender, race) and existing comorbidities (e.g., congestive heart failure, diabetes, chronic kidney disease)
	Blended Census Reporting Tool (BCRT) data (UHC members only)	real-time inpatient admission data including ICD-10 diagnosis codes, discharge status, COVID test status reviewed by UHC's clinical team; will be used as complementary to Optum infusion pharmacy data for COVID hospitalizations
	Clinical Data Services Management (CDSM) data (UHC members only)	SARS-CoV-2 lab testing data from reporting health systems, clinics, and third-party labs; will be used as complementary to Optum infusion pharmacy data for COVID tests
Potential pool of controls	Optum EMR data	primary source to confirm for presence of symptoms during COVID+ test of a matched individual (analogous to the symptoms collected as part of ProtectWell data for study participants); will also be used for COVID test status and COVID hospitalization of all potential controls, and for demographic characteristics, existing comorbidities, COVID test status and COVID hospitalization of potential non-UHC controls.
	UHC claims data (UHC members only)	data including demographic characteristics (e.g., age, gender, race) and existing comorbidities (e.g., congestive heart failure, diabetes, chronic kidney disease)
	Blended Census Reporting Tool (BCRT) data	real-time inpatient admission data including ICD-10 diagnosis codes, discharge status, COVID test

LY3819253

(UHC members only)	status reviewed by UHC's clinical team; this dataset does not include symptom information during COVID test, hence it will be only used as a potential sensitivity analysis data source

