4.5 Endpoints

The following definitions of endpoints hold for all analyses described in this statistical analysis plan. For study participants, we define the study endpoint as 28 days after date of the Bamlanivimab infusion. This holds for both outcomes of COVID-related hospitalization with or without time consideration (i.e., no censoring vs censoring at Day 28). For example, if a study participant hasn't been hospitalized due to COVID-19 within 28 days after COVID-19 diagnosis, we'll treat the binary response of COVID-19 hospitalization as 0 without time consideration. However, with time consideration, it becomes right-censored since this participant may be hospitalized 29 or more days after COVID-19 diagnosis and our observation period is 28 days after COVID-19 diagnosis. More details are described in Section 5.8.1.3. For the pool of potential controls, we define the study endpoint as 28 days after a synthetic date of treatment. We will randomly select a number from the distribution of number of days after date of symptoms onset in study participants to identify an index date with which to define 28 days post infusion where we will monitor claims and EMR data for hospitalizations and mortality.

Commented [WWY14]: Should be the pool of controls which was before PS matching.

Figure 3 illustrates the timeline for study participants and controls to ensure alignment on an index date for symptoms onset and the follow-up period. Since the control group will not have an infusion date associated with them, we will randomly select a number from the distribution of number of days after date of symptoms onset in study participants to identify an index date with which to define 28 days post infusion where we will monitor claims and EMR data for hospitalizations and mortality.

[figure not shown]

Figure 3. Illustration of the timeline for study participants and controls.

For patients who do not experience a COVID-19 related hospitalization by Day 28 following the date of infusion or synthetic treatment, a censoring date is defined as the earliest of 28 days following the date of treatment, or for study participants, the early discontinuation date due to lost to follow-up.

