5.4 Participant Dispositions – Study Participants Group Only

The number and percentage of study participants who complete the study or discontinue early will be tabulated by 28 days. Here, we consider that the subset of study participants for whom outcome data can be obtained through UHC claims, Optum EMR, or Optum infusion pharmacy data sources during the 28 days post-infusion time period are completing the study, whereas remaining subset of study participants for whom outcome data cannot be confirmed by any of these data sources during the 28 days post-infusion time period are discontinuing early. All patients who enter the study and discontinued from the study will be listed, and if available, the timing (from receiving study treatment) and reason of discontinuing the study will be reported.

Commented [XM24]: The number and percentage of study participants who complete the study or discontinue early will be tabulated by 28 days. Reasons for discontinuation will be summarized.

All patients who enter the study and discontinued from the study will be listed, and the timing of discontinuing (from receiving study treatment) the study will be reported. If known, a reason for their discontinuation will be given.

In addition, a graphical summary (i.e., KM plot) of time from study treatment to early permanent discontinuation of study due to AEs may be generated if there are a substantial number of such events.

Commented [XM25]: Please add sections:

- Multiple Comparisons/Multiplicity
- Patient Characteristics
- Prior Medication and Concomitant Therapy
- Protocol Violations

Commented [WWY26R25]: Refer to attached sample SAP

Commented [JAT27R26]: Added the new section 5.7.

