In the short term, we will use Optum infusion pharmacy data and BCRT data to identify hospitalization among the treatment group; and we will use UHC claims data and Optum EMR data for inpatient records for identification of COVID-related hospitalizations among the control group. We will evaluate treatment effects based on a two-sided test with a level of 0.05 for all efficacy analyses, and provide 95% confidence intervals for the odds ratio/hazard ratio.

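### SAP 5.4 judges completion of follow-up from a source list that omits BCRT and ProtectWell, so completion can be miscounted; if that status also sets the participants-only censoring date, the time-to-event results can be biased

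*SAP*

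**What the plan says.** - **Disposition (SAP 5.4).** A participant counts as a completer when "outcome data can be obtained through UHC claims, Optum EMR, or Optum infusion pharmacy data sources during the 28 days post-infusion time period". Those for whom "outcome data cannot be confirmed by any of these data sources during the 28 days post-infusion time period are discontinuing early". No rule sets a discontinuation date; "if available, the timing (from receiving study treatment) and reason of discontinuing the study will be reported".
- **Censoring (SAP 4.5).** A patient with no COVID-19 hospitalization by Day 28 is censored at the earlier of Day 28 "or for study participants, the early discontinuation date due to lost to follow-up". Controls have no early-censoring clause.
- **Finding participants' admissions (SAP 5.8.1.3).** In the short term, "we will use Optum infusion pharmacy data and BCRT data to identify hospitalization among the treatment group".
- **Scheduled follow-up (SAP 4.2, Table 1).** ProtectWell supplies "Day 1-28 wellness tracking (in numeric 1-10 ratings" for infused participants.
- **Controls (SAP 4.2).** "We require matched controls to remain enrolled in utilized data sources to assure data availability".
- **Drop-out fields.** Protocol 4.4, Phase II.B, collects "Drop-out date (If available" and a drop-out reason. SAP 4.7, Phase II.B, lists neither, and SAP 5.14 records no change from the protocol's analyses.

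**The concern.** Whether someone has been followed to Day 28 should not depend on whether something happened to them. Admitted people generate records, whereas people who stay well may not. SAP Appendix 2 says the post-infusion pharmacy form is completed when a participant has symptoms, an infusion reaction or an adverse event, so a well participant may have no pharmacy entry after Day 1.

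For non-UHC participants the list is thinner still. Table 1 restricts claims and BCRT to UHC members and shows Optum EMR only for the control pool, which leaves the pharmacy data alone. SAP 5.8.1.2 plans to match these participants, although SAP 5.1.1 says all analysis populations are UHC members.

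Two outputs are exposed. The disposition table can misreport completion. If the same status feeds the 4.5 censoring date, one group can be censored in a way that depends on outcome while the other runs to Day 28. That would affect the Kaplan-Meier curves, the log-rank test and the adjusted hazard ratio planned for Table A9.

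**Working it through.** **1. Sources side by side**

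| Source | In the 5.4 list | Participant source in Table 1 | Named in 5.8.1.3 text for participants' admissions |
|---|---|---|---|
| UHC claims | yes | yes, UHC only | no (named for controls) |
| Optum EMR | yes | no (control pool only) | no (named for controls) |
| Infusion pharmacy | yes | yes | yes |
| BCRT | no | yes, UHC only | yes |
| ProtectWell | no | yes | no |

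Only one of the three sources that define completion is named in that text for participants' admissions.

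**2. The plan's own figures.** The documents give no rate of loss or censoring to reproduce. The scenario used below is the one in SAP 4.4.2: 15% against 10%, 1,000 per group, power 0.8, two-sided 0.05. It checks: n = [1.96·√(2·0.125·0.875) + 0.842·√(0.15·0.85 + 0.10·0.90)]² / 0.05² = 686 per group (726 with continuity correction). Power at 1,000 per group is about 0.92, so the plan's figure is conservative.

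**3. Kaplan-Meier effect if well participants are censored early.** Assumptions not in the documents: a fraction f of event-free participants is censored after Day 1, all events fall on Days 2 to 28, and every event is kept. With 1,000 participants and 100 events, 900f leave the risk set before any event. The Day 28 estimate is 100/(1,000 − 900f) = 0.10/(1 − 0.9f). The apparent reduction is 1 − estimate/0.15.

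| f | Estimate | Apparent reduction from 15% |
|---|---|---|
| 0 | 10.0% | 33% |
| 5% | 100/955 = 10.5% | 30% |
| 10% | 100/910 = 11.0% | 27% |
| 20% | 100/820 = 12.2% | 19% |
| 30% | 100/730 = 13.7% | 9% |

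**4. Hazard ratio and the assumed date.** A Cox model was fitted to expected-count cohorts at 15% and 10%, with standard errors scaled to 1,000 per group. Paired values are for events spread evenly / concentrated early.

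| f | Censoring day | HR | Upper 95% limit |
|---|---|---|---|
| 0 | none early | 0.65 / 0.65 | 0.84 / 0.84 |
| 10% | Day 1 | 0.72 / 0.71 | 0.92 / 0.91 |
| 20% | Day 1 | 0.80 / 0.78 | 1.02 / 1.01 |
| 20% | Day 7 | 0.76 / 0.70 | 0.98 / 0.90 |
| 20% | Day 14 | 0.72 / 0.67 | 0.93 / 0.86 |
| any | Day 28 (no date) | 0.65 / 0.65 | 0.84 / 0.84 |

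**5. Direction.** Suppose instead that the unconfirmed group hides admissions (early-concentrated events, censored at Day 1). Losing about 10% or 20% of participants' events gives HR 0.59 or 0.53, in the drug's favour. With 20% of event-free participants censored at Day 1 and 20% of events lost, HR is 0.64, close to the true 0.65.

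**6. Binary endpoint.** In steps 3 and 4 the participants' binary Day 28 rate stays at 10.0% throughout, because censoring does not enter it.

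**The case against.** A reader might infer that the plan's time-to-event result is biased against the drug. The documents do not support that, for four reasons.

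- **No stated link.** SAP 4.5 refers to loss to follow-up and does not cite 5.4, which is a disposition section. Using 5.4 for the censoring date is an inference, though a natural one, since no other definition is given.
- **What counts as confirmed.** SAP 5.4 does not require a positive record. For an enrolled UHC member, claims showing no admission can be read as outcome data. On that reading most well UHC participants are completers, and the problem falls mainly on non-UHC participants. The SAP does not state this reading.
- **Date.** A participant with no discontinuation date defaults, under the earlier-of rule in 4.5, to Day 28, with no bias. Day 1 is close to the worst case.
- **Direction.** Missed admissions push the other way.

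Three further points are fair. A BCRT-only admission is still an event under 4.5 and is not censored, so that example affects only the disposition table; its claim may also arrive later. ProtectWell records wellness ratings rather than admissions, so leaving it off a list of outcome sources is defensible, though it does show who was still in contact. SAP 5.4 also still promises timing and reason where available, and the protocol's drop-out date carries the same qualifier.

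These points limit the size and settle that the direction is conditional. They do not reconcile the 5.4 list with 5.8.1.3, supply a date rule, or give the two groups the same rule.

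**Conclusion.** The point holds in a limited form. SAP 5.4 is inconsistent with the sources the SAP uses elsewhere for participants, and applied as written it can misstate the completion rate. Bias in the Kaplan-Meier, log-rank and Cox results is possible but conditional: it requires the 5.4 status to be used for the 4.5 censoring date and a date before Day 28 to be assigned.

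If the unconfirmed participants are mainly well, the bias runs against the drug. At the near-worst Day 1 date, with 5 to 30% affected, a 10% risk reads as 10.5 to 13.7%. With 20% affected, the hazard ratio moves from 0.65 to about 0.80 and its upper limit just passes 1, but at Day 14 it is only 0.67 to 0.72. The affected share and the date are assumptions; the documents give neither. The binary primary endpoint is not altered by this rule. The matter should be settled before outcome data are accessed.

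**What to change.** 1. Add BCRT and ProtectWell to the SAP 5.4 source list.
2. State that a UHC participant enrolled through Day 28 with no admission found is followed to Day 28, the same rule as for controls.
3. Censor early only at a dated event: consent withdrawal, loss of enrolment or, for non-UHC participants, documented loss of contact. Make SAP 4.5 refer to this rule.
4. Restore the protocol's drop-out date and reason to SAP 4.7, Phase II.B.
5. Add a sensitivity analysis carrying all event-free participants to Day 28.

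**Cost.** SAP wording, plus enrolment dates, check-ins and drop-out fields that the study already plans to hold. The downside concerns non-UHC participants: self-reported check-ins are weaker confirmation than claims, and censoring at the last check-in could hide an admission that stopped the check-ins, which would favour the drug. That result should be read alongside the sensitivity analysis in item 5.

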5.5 Patient Characteristics

Patient demographic variables and baseline characteristics (listed in Section 4.7) will be summarized by participant status and the overall population. The continuous variables will be summarized using mean with standard deviations or median with interquartile range, and the categorical variables will be summarized using frequency count and percentage. Difference between study participants and controls will be tested by *t*-test or Wilcoxon rank sum test for continuous variables and chi-squared test for categorical variables. Baseline characteristics included in the propensity score model and prognostic score model will be summarized for the propensity matched population and double score matched population.

5.6 Treatment Compliance

Participants will receive study intervention directly from the investigator or qualified designee, under medical supervision. The date of infusion will be recorded in the source documents and recorded in the CRF. Treatment compliance will not be reported.

5.7 Prior Medication and Concomitant Therapy

According to the EUA, we consider immunosuppressive medications 6 months prior to date of COVID-19 diagnosis as a potential risk factor of COVID-19 hospitalization. Additional descriptive summaries on prior medications and concomitant therapies could be provided for study participants and matched controls if available.

5.8 Primary Analysis

The main objective is to determine the incidence of COVID-related hospitalization at Day 28 among Bamlanivimab-treated participants relative to external controls. We separate the primary analysis into three parts – identify risk factors of COVID-related hospitalization as matching covariates, match controls for study participants, and compare the COVID-related hospitalization rate between study participants and matched controls.

5.8.1 Main analytical approach

5.8.1.1 Pre-matching identification of risk factors as matching covariates

Before matching, we will select covariates to be included in the propensity score estimation model. Covariates that are predictive of both treatment status and the outcomes and covariates that are associated with the outcomes will be selected to estimate propensity score. To do so, we will first conduct a literature review to identify the risk factors that are associated with COVID-19 hospitalization. The findings from the literature review will help create a list of variables on which treatment and control groups will be matched.

Consider a binary response taking a value of 1 if a patient is hospitalized due to COVID-19, and 0 if a patient is tested positive for SARS-CoV2 but does not have a record of subsequent COVID-related hospitalization (hospitalization within 38 days of a positive test). We include risk factors such as demographic (e.g., gender, age, race, geographical area such as state or county), comorbidities (Elixhauser scores related comorbidities such as diabetes, metastatic cancer, heart diseases, obesity, coagulopathy, and so on), and other potential clinical attributes as available in

the identification of the appropriate matched cohort. These risk factors will also include all clinically identified variables by Eli Lilly to define moderate and high-risk groups. We will run this step three times with three datasets; specifically, we consider:

- a. Iteration 1: This is based on retrospective data available in-house consisting of Medicare Advantage (MA) members, aged greater than or equal to 65, and COVID diagnosed. We will exploit BCRT, CDSM, and UHC Claims data sources. The study cohort here is a broader population than the study participants.
- b. Iteration 2: This is solely based on data associated with study participants. We will exploit risk factors from UHC Claims and study enrollment information from Optum infusion pharmacy data.
- c. Iteration 3: This is based on information of both the general MA population and study participants –retrospective and prospective data in Iteration 1 and Iteration 2, respectively. We will exploit COVID labs and hospitalizations from BCRT and CDSM, risk factors from UHC Claims data, and study enrollment information from Optum infusion pharmacy data.

We will identify the covariates that are consistent across all three iterations and select the final set based on data, literature, and clinician decision. The main objective of this initial iteration step is to reduce dimension, exclude noise variables, include clinically meaningful variables, and lay out the foundation for the subsequent analyses. We will develop a generalized linear (mixed) model (Nelder, 1972) (McCulloch, 2014) with a logit link function to quantify the association and make inferences about the parameter estimates based on the retrospective data. The appropriateness of using random effects (e.g., region or state of residence) will be evaluated by the likelihood ratio test (LRT) and summary information criteria (e.g., conditional or marginal Akaike information criteria (AIC)). Model performance will be evaluated by conditional (pseudo) R-square, Somers' Dxy, and C-statistic. We will select influential risk factors in the light of both clinical relevance and statistical significance. In this pursuit, we will use GL(M)M with a Least Absolute Shrinkage and Selection Operator(LASSO) (Tibshirani, 1996) to develop a parsimonious model; here, the optimum parameters will be selected by k -fold cross-validation with the 1-standard-error rule. We will also check the statistical significance of any association based on Wald test statistic between each covariate and response based on univariate and multivariate GL(M)M; a pre-determined threshold of, say 0.10 (level of significance), will be used to select covariates. This sequential inferential approach (i.e., Wald) is supplementary to the regularization step (i.e., GL(M)M-LASSO), and the final set of covariates will be determined by exploiting both/either approaches and will be combined with clinical relevance.

Commented [XM28]: Which variables will be considered as random variables?

Commented [JAT29R28]: Added in the main texts.

Commented [XM30]: Using R or SAS?

Commented [JAT31R30]: R. Also added software information in Section 5.1, General Considerations.

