We will identify the covariates that are consistent across all three iterations and select the final set based on data, literature, and clinician decision. The main objective of this initial iteration step is to reduce dimension, exclude noise variables, include clinically meaningful variables, and lay out the foundation for the subsequent analyses. We will develop a generalized linear (mixed) model (Nelder, 1972) (McCulloch, 2014) with appropriately chosen link functions to quantify the association and make inferences about the parameter estimates based on the retrospective data. The appropriateness of using random effects will be evaluated by the likelihood ratio test (LRT) and summary information criteria (e.g., conditional or marginal Akaike information criteria (AIC)). We will select influential risk factors in the light of both clinical relevance and statistical significance. In this pursuit, we will use GL(M)M with a Least Absolute Shrinkage Penalty (LASSO) (Tibshirani, 1996) to develop a parsimonious model; here, the optimum parameters will be selected by k -fold cross-validation with the 1-standard-error rule. We will also check the statistical significance of any association based on Wald test statistic between each covariate and response based on univariate and multivariate GL(M)M; a pre-determined threshold of, say 0.10 (level of significance), will be used to select covariates. This sequential inferential approach (i.e., Wald) is supplementary to the regularization step (i.e., GLMM-LASSO), and the final set of covariates will be determined by exploiting both/either approaches and will be combined with clinical relevance (i.e., factors used in determining high, moderate, low risk groups by Lilly).

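### The propensity covariates are chosen partly by modelling participants' hospitalization, although the protocol requires matching before outcome data are opened; the SAP leaves this conflict unresolved

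*SAP*

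**What the plan says.** SAP 5.8.1.1 takes COVID hospitalization as the response of a covariate screen, with non-events defined by the absence of "hospitalization within 38 days of a positive test". The screen is run on three datasets.

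- Iteration 1 uses retrospective Medicare Advantage data.
- "Iteration 2: This is solely based on data associated with study participants".
- Iteration 3 combines the two, retrospective and prospective, and draws on "COVID labs and hospitalizations from BCRT and CDSM, risk factors from UHC Claims data, and study enrollment information from Optum infusion pharmacy data".

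Selection uses LASSO tuned by "cross-validation with the 1-standard-error rule", with a supplementary Wald screen at 0.10. The results are combined as follows: "We will identify the covariates that are consistent across all three iterations and select the final set based on data, literature, and clinician decision". Protocol 6.5.1.1 has the same three iterations and the same opening rule: "We will identify the covariates that are consistent across all three iterations".

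SAP 5.8.1.2 puts the selected risk factors into the propensity model and schedules matching after the 28-day study period.

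Three passages bear on outcome access:

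- Protocol 6.5.1.2 requires the 1-to-1 match to be in place before outcome data are opened. The parallel sentence in SAP 5.8.1.2 stops at the 1-to-1 match and does not carry this condition.
- SAP 5.8.1.3, like protocol 6.5.2, requires one outcome model to be chosen and documented before outcome data are opened.
- SAP 5.2 has the adjustment list confirmed before the outcome analyses start, and adds to it any risk factors found by the Section 5.8 regression.

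SAP 5.14, which should list changes from the protocol, gives none.

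**The concern.** The study is not randomized, so the credibility of its primary comparison rests on how the control group was formed. The usual protection is to fix the match without sight of the outcome. Here matching comes after follow-up has ended, so the outcomes already exist and only a written lock can keep them unseen.

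The plan instead sends participants' hospitalizations through the step that decides what to match on. Several choices are still open after that step: the final covariate set, which depends partly on judgement; the caliper, whose size is set empirically; and repeated matching until balance is reached. A reader of the results could not verify that none of these was influenced by the events already seen.

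**Working it through.** No stated figure is in dispute. The check compares passages, with one piece of arithmetic.

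1. **Does the screen use the primary outcome?** The response is COVID hospitalization. Participants are tested after reporting symptoms. Infusion follows a positive test and falls within 10 days of symptom onset (protocol 6.1). Follow-up is 28 days from infusion. The latest end of follow-up is therefore 10 + 28 = 38 days after onset, which is the 38-day limit in protocol 4.2 and SAP 4.2. The test is no earlier than onset, so the end of follow-up is at most 38 days after the test. If onset is taken as two days before diagnosis, as a margin note in SAP 4.7 does, the figure is 10 − 2 + 28 = 36 days. Either way, the 38-day screening window contains the whole primary endpoint window.

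2. **Are participants' outcomes used?** For Iteration 3 this is explicit: hospitalizations are a named input, and the participants' prospective data are included. For Iteration 2 it is an inference. Its source list names only claims risk factors and enrollment information. However, one response definition serves all three runs. SAP Table A5, a table of risk factors for COVID hospitalization, also has a study-participant column for test statistics or odds ratios. That column cannot be filled without participants' hospitalizations.

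3. **Are controls' outcomes used as well?** SAP Table 3 lists pre-matching identification of risk factors as a use of the pool of potential controls. The caption of Table A5 describes its first cohort as UHC members who meet the study's eligibility criteria. Outcomes on both sides may therefore be read before matching.

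4. **Does the screen come before the match and shape it?** Yes. It is headed as a pre-matching step, and SAP 5.8.1.2 takes the propensity covariates from it.

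5. **Can the protocol's rule be kept?** No. Protocol 6.5.1.1 needs participants' hospitalizations to choose the matching covariates; 6.5.1.2 requires the match before such data are opened. The protocol contradicts itself.

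6. **Does the SAP resolve this?** No. It repeats the screen and leaves out the condition. The rule in 5.8.1.3 governs the outcome model, not the match. The screen weakens that rule too, because 5.2 lets the Section 5.8 regression add variables to the outcome model. The lock in 5.2 comes only before the outcome analyses, after the screen has been run.

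7. **Is there another route to outcomes before the lock?** Table A4 sets participants beside the unmatched pool and includes a row for Day 1–28 hospitalization. The SAP does not say that this row waits until matching is final.

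**The case against.** **Participants' outcomes may not be meant.** Iteration 2 names no hospitalization source, and 5.8.1.1 says inference is based on the retrospective data. This stands to the extent that outcome access in Iteration 2 is inferred. It does not remove Iteration 3 or the participant column in Table A5.

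**The SAP did not create the problem.** This stands. The conflict begins in the protocol, the SAP changed no planned screen, and nothing in it revokes the protocol's clause. The empty entry in 5.14 is a reporting gap about one omitted condition. A reader might infer that the SAP abandoned outcome blinding altogether; 5.8.1.3 shows that it did not.

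**No bias is shown.** This also stands. Everyone in Iteration 2 is treated, Table A5 lists no treatment term, and re-matching is tied to covariate imbalance. A reader might infer a biased treatment effect, but the documents do not support that.

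**The three-way filter may lose true confounders.** A reader might infer this because the participant-only fit is the smallest. The plan does not define what counts as consistent, and it keeps other routes into the set. On the literature review: "The findings from the literature review will help create a list of variables on which treatment and control groups will be matched". On the selectors: "the final set of covariates will be determined by exploiting both/either approaches and will be combined with clinical relevance". SAP 5.2 also adjusts for all qualifying risk factors. Any figure for lost factors would depend on one reading of the rule and on risk structures the documents do not give, so none is offered.

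**Conclusion.** The plan is wrong as written: two protocol instructions cannot both be followed, and the SAP repeats one while omitting the other. The conclusion rests on the texts and the 38-day arithmetic. Its only inference is that Iteration 2 uses the common response, and Iteration 3 is enough without it.

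The size is one of design integrity. Two of the three selection runs include the participants' primary-endpoint events, and Table 3 opens the control side as well. No numerical effect on the treatment estimate can be derived from the documents. The point should be fixed before any matching, but it does not by itself invalidate the comparison.

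**What to change.** Change the protocol and SAP together.

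1. Choose the propensity covariates from the literature review, the pre-identified clinical risk factors and Iteration 1. Run Iteration 1 on historical data that exclude both study participants and the eligible control pool. Correct SAP Table 3 to agree.
2. Remove Iterations 2 and 3 from covariate selection. They may be run descriptively once the match is locked.
3. Restore the protocol's condition in SAP 5.8.1.2. Covariates, caliper and matched pairs are fixed before Day 28 hospitalization data for participants or candidate controls are accessed for analysis. Exempt the admission data needed to apply eligibility and the ongoing safety review. Produce the Table A4 hospitalization row after the lock.
4. SAP 5.13 runs the primary analysis on the first 1,000 participants, so later matching would follow outcome access. Fix the covariate list and matching algorithm before that analysis and apply them unchanged to later participants.
5. Take the SAP 5.2 adjustment list from the same locked set, and record the change in 5.14.

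The double-score sensitivity analysis in SAP 5.8.2 uses control outcomes by design if its prognostic model is fitted to the control pool; it would then follow the lock.

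The cost is rewording, plus separating the historical data from the eligible control pool. No new data element is needed. The propensity model may be larger and some more participants may go unmatched; this cannot be computed, because the size of the control pool is not given.
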